5.2.8 Conditions for Withdrawal

Subjects will be informed that they have the right to withdraw from the trial at any time.

A subject may be withdrawn from the study:

- At the discretion of the Investigator or Sponsor due to safety concerns (withdrawal) without the subject's permission
- At the request of the subject (dropout)

The following will result in automatic withdrawal or exclusion of a subject from the study:

- Significant non-compliance with the protocol, based on the Investigator's judgment

The reason for a withdrawal or dropout should be clearly documented in the source documents and on the CRF.

The Investigator must determine whether voluntary withdrawal is due to safety concerns (in which case, the reason for discontinuation will be noted as "SAE" or "other AE" as appropriate) or for another reason.

Withdrawn subjects will not be replaced.

5.2.9 Lost to Follow-up Procedures

In the case of subjects who fail to return for a follow-up examination, documented reasonable effort (i.e., at least 3 documented telephone calls on different days and certified mail) should be undertaken to locate or recall them, or at least to determine their health status while fully respecting their rights. These efforts should be documented in the CRF and in the source documents.

5.2.10 Classification of Subjects Who Discontinue the Trial

For any subject who discontinues the trial prior to completion, the most significant reason for early termination will be checked in the CRF. Reasons are listed below from the most significant to the least significant (refer to the CRF completion guidelines for additional details and examples):

- **Serious adverse event:** To be used when a subject drops out of or is withdrawn from the study by the Investigator because of the occurrence of an SAE, as defined in [Section 9.2.1](#)
- **Other adverse event:** To be used when a subject drops out of or is withdrawn from the study by the Investigator because of the occurrence of an AE other than an SAE, as defined in [Section 9.2.1](#)
- **Non-compliance with protocol:** To be used when the Investigator withdraws a subject from the study because of failure to follow the protocol, including when it is retrospectively discovered that a subject did not fulfill the eligibility criteria. (e.g., not attending visits, not being available for telephone calls, not providing blood samples). The Investigator will provide a comment as to the specific cause of non-compliance.
- **Lost to follow-up:** To be used when the Investigator withdraws a subject from the study because of failure to establish contact, as outlined in [Section 5.2.9](#). The Investigator will provide documentation that contact was attempted (i.e., return of unsigned certified letter receipt).
- **Voluntary withdrawal not due to an adverse event:** To be used when a subject drops out of the study for any reason other than those listed above.

5.2.11 Follow-up of Discontinuations

The site should complete all scheduled safety follow-ups and contact any subject who has prematurely terminated the trial because of an SAE, other type of AE, non-compliance with the protocol, or loss of eligibility, including definite contraindications.

For subjects where the reason for early termination was lost to follow-up or if the subject withdrew informed consent and specified that they do not want to be contacted again and it is documented in the source document, the site will not attempt to obtain further safety information.

When early termination is due to an AE or SAE, loss of eligibility, non-compliance with the protocol including definite contraindications, the subject will be contacted.

For subjects where the reason for early termination is voluntary withdrawal, the site will attempt to contact them by V08 (6-month following the last planned vaccination), except if they specified that they do not want to be contacted again and it is documented in the source document.

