5.2.7.2 Definitive Contraindications

Should a subject experience one of the conditions listed below, the Investigator will discontinue vaccination:

- Pregnancy, as indicated by a positive urine test
- Anaphylactic or other significant allergic reaction to the previous dose of vaccine
- Immunoglobulin, blood or blood derived products received in the past 3 months or ongoing at the visit
- Immunosuppressive therapy such as anti-cancer chemotherapy or radiation therapy in the past 6 months or ongoing at the visit, or long-term systemic corticosteroid therapy (for more than 2 consecutive weeks in the past 3 months before the visit)
- HIV seropositivity
- Thrombocytopenia, bleeding disorder or receipt of anticoagulants contraindicating IM vaccination
- Administration of a vaccine other than the study vaccine between D0 and V06 (VAC5+14D)
- An SAE related to the trial vaccines following a vaccination.
- Any potential contact with rabies virus during the course of the study.
- Reporting of Guillain-Barré syndrome

Subjects will not be withdrawn due to contraindication but will be followed up for safety and possibly immunogenicity assessment.

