9.2.2 Safety Endpoints

The primary endpoint(s) for the evaluation of safety are:

- Occurrence of any unsolicited systemic adverse events (AEs) reported in the 30 minutes after each vaccine injection

Collection of injection site reactions:

- Occurrence of solicited (prelisted in the subject's diary card [DC] and electronic case report form [CRF]) injection site reactions occurring within 7 days after each injection
- Occurrence of unsolicited (spontaneously reported) injection site reactions occurring within 28 days after each injection

Collection of systemic reactions and AEs:

- Occurrence of solicited (prelisted in the subject's DC and CRF) systemic reactions between the first and the second injections as well as between the second and the third injections, and up to 7 days after the remaining injections.
- Occurrence of unsolicited (spontaneously reported) systemic AEs between each injection and up to 28 days after the last injection.
- Occurrence of serious adverse events (SAEs) throughout the trial.

Other endpoints recorded or derived will be described at the time of statistical analysis plan. Depending on the item, these could include: nature (Medical Dictionary for Regulatory Activities [MedDRA] preferred term), time of onset, duration, number of days of occurrence, grade of severity, relationship to vaccine, action taken, whether the AE led to early termination from the study, seriousness, or outcome.

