|-----------------|--|----------------|
| Post-dose 3,4,5 | | D0-D3 D4-D7 |
|-----------------|--|----------------|

- Range of number of days of occurrence categories are in Table 5.3

Table 5.3: Range of Number of Days of Occurrence Categories for Solicited Reactions during the solicited period

| | Injection Site Reactions | Systemic Reactions |
|------------------|------------------------------------|--------------------------|
| Post-dose 1 | 1 - 3 days 4 - 7 days 8 days | 1 - 3 days 4 days |
| Post-dose 2 | | 1 - 3 days 4 - 5 days |
| Post-dose 3, 4,5 | | 1 - 3 days 4 - 7 days |

Solicited reaction after any injection

“After any injection” means after the five scheduled vaccine injections, and at least after the first vaccine injection (D0).

The solicited reaction will be presented after any injections according to:

- Overall occurrence over the D0-D7 period for injection site reactions or between vaccinations for systemic reactions (up to D7 for the last 2 vaccinations)
- Time of onset period
- Intensity grade: the maximum intensity grade will be computed during the solicited period for all solicited reactions and overall for on-going solicited reactions.

30-minutes Post-Vaccination Observation Period

Unsolicited systemic AEs occurring within 30 minutes after each vaccination will be presented in summary safety tables, analyzed according to their nature (SOC and PT of the MedDRA classification) and will be listed.

Unsolicited Adverse Events

The unsolicited non-serious AEs will be analyzed

- “Between the first and the second vaccine injection”, which corresponds to AEs reported at V02 and occurring after the first vaccine injection †

† For subjects interrupting their vaccination schedule after the first injection, unsolicited AEs until 28 days after the first injection are collected at visit V02

- “Between the second and the third vaccine injection”, which corresponds to AEs reported at V03 and occurring after the second vaccine injection [†]
- “Between the third and the fourth vaccine injection”, which corresponds to AEs reported at V04 and occurring after the third vaccine injection [§]
- “Between the fourth and the fifth vaccine injection”, which corresponds to AEs reported at V05 and occurring after the fourth vaccine injection ^{**}
- “Within 28 days after the fifth vaccine injection”, which corresponds to AEs reported at V07 and occurring after the fifth vaccine injection

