- “Within 28 days after any vaccine injection”, which corresponds to AEs belonging to any of the five above categories

An AE reported with an onset > 28+3 days after an injection will not be included in the analysis, but will be listed separately. The unsolicited AEs will be summarized in the safety overview and analyzed according to their nature (SOC and PT of the MedDRA classification), causality (relationship to the vaccine injection as assessed by the investigator), time of onset, duration and maximum intensity.

The occurrence of any unsolicited non-serious AE will be presented after any and each injection according to:

- *Maximum intensity:*

- Missing
- Grade 1
- Grade 2
- Grade 3

- *Time of onset categories*

- Missing
- D0-D3
- D4-D7
- D8-D14
- >=D15

[†] For subjects interrupting their vaccination schedule after the second injection, unsolicited AEs until 28 days after the second injection are collected at visit V03

[§] For subjects interrupting their vaccination schedule after the third injection, unsolicited AEs until 28 days after the first injection are collected at visit V04

^{**} For subjects interrupting their vaccination schedule after the fourth injection, unsolicited AEs until 28 days after the second injection are collected at visit V05

- *Maximum duration:*

- Missing
- 1 - 3 days
- 4 - 7 days
- 8 - 14 days
- 15 days or more

SAEs and AESIs

The SAEs and AESIs occurred during the study will be analyzed on the following periods:

1. vaccination period: after any vaccination period (D00-D56[+3D])
2. during the six-month safety follow-up period (all SAEs and AESIs from D56[+3D])

SAEs will be analyzed according to their causality (relationship to vaccine injection as assessed by the investigator), seriousness, outcome and nature (SOC and PT of the MedDRA classification).

AESIs will be summarized and analyzed according to their nature (SOC and PT of the MedDRA classification) and causality.

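### Protocol 5.2.11 lets the first contact with a voluntary withdrawal fall about 5 to 6 months after the 28-day AE window closes, while the SAP keeps that subject in the unsolicited-AE denominator

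*Protocol*

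**What the plan says.** Protocol 5.2.11 sets three levels of follow-up, according to the reason for leaving.

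- **SAE, other AE, non-compliance or loss of eligibility:** full follow-up. "The site should complete all scheduled safety follow-ups and contact any subject who has prematurely terminated the trial because of an SAE", and the sentence goes on to the other reasons in this group.
- **Lost to follow-up, or consent withdrawn with a documented wish for no contact:** none. In these cases "the site will not attempt to obtain further safety information".
- **Other voluntary withdrawals:** "For subjects where the reason for early termination is voluntary withdrawal, the site will attempt to contact them by V08". The section dates V08 as six months after the last planned vaccination.

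The endpoint in Protocol 9.2.2 is "Occurrence of unsolicited (spontaneously reported) systemic AEs between each injection and up to 28 days after the last injection".

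Footnotes in SAP 5.1.2.2.1 cover subjects who stop the injections early. After dose 1: "For subjects interrupting their vaccination schedule after the first injection, unsolicited AEs until 28 days after the first injection are collected at visit V02". After dose 2: "For subjects interrupting their vaccination schedule after the second injection, unsolicited AEs until 28 days after the second injection are collected at visit V03". After dose 3 the reference point changes: "For subjects interrupting their vaccination schedule after the third injection, unsolicited AEs until 28 days after the first injection are collected at visit V04". The dose-4 footnote counts 28 days from the second injection.

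The same SAP section says that the denominator will be subjects with documented safety, so that incidences are not under-estimated. For unsolicited events it then defines the denominator as all subjects vaccinated at the dose, or at least once for the any-dose analysis. For solicited reactions it uses subjects with non-missing data. SAP 5.3.2 replaces no missing safety data and expects very little of it.

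**The concern.** The AE window is tied to the last injection received, but the only contact rule for this group is tied to the last injection planned. The earlier a subject leaves, the longer the permitted gap.

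The diary card may be out of reach too. According to the Table of Study Procedures, DC1 is collected at V04, DC2 at V05 and DC3 at V07. A subject who leaves between visits still holds an open card, and nothing schedules its return. The SAP files the AEs of a dose-1 stopper under V02, which is D3. A record running to 28 days therefore needs some later contact, and the protocol sets no date for one in this group short of V08.

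What is at stake is the unsolicited-AE rate. A vaccinated subject with no follow-up adds one to the denominator and nothing to the numerator. Safety is one of the inputs to the choice of VRVg-2 dosage (Protocol section 12). An AE first learned of near V08 could also arrive too late for the D0–D56 analysis, although the lock date is not given.

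**Working it through.** **The plan's own figure.** Protocol Table 12.2 gives 8/80 = 10.0% with a 95% CI of 4.4 to 18.8. Clopper-Pearson limits from beta quantiles reproduce this and the other four rows to one decimal. The table is not in dispute; it serves as the yardstick for size.

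**Timing.** Inputs are injections on D0, D3, D7, D14 and D28, and V08 six months after the D28 injection (Protocol Table 5.3). Taking 6 months as 182 days (an assumption), V08 = 28 + 182 = D210. The 28-day window closes at injection day + 28.

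| Last dose received | Window closes | Days from last dose to V08 | Days from window closing to V08 |
|---|---|---|---|
| 1 (D0) | D28 | 210 | 182 |
| 2 (D3) | D31 | 207 | 179 |
| 3 (D7) | D35 | 203 | 175 |
| 4 (D14) | D42 | 196 | 168 |
| 5 (D28) | D56 | 182 | 154 |

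With 6 months taken as 180 to 184 days and the ±14-day visit window, the last column becomes 166 to 198 days for dose 1 and 138 to 170 days for dose 5.

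**Footnote windows as written.** Stop after dose 3: 28 days from the first injection is D28, and 28 − 7 = 21 days after dose 3. Stop after dose 4: 28 days from the second injection is D3 + 28 = D31, and 31 − 14 = 17 days after dose 4. Neither reaches the 28 days after the last injection in Protocol 9.2.2.

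**Effect on an unsolicited-AE rate.** Let p be the true rate and m the number of 80 vaccinated subjects with no post-dose AE data who stay in the denominator. If the uncollected subjects resemble the others, the expected reported rate is p × (80 − m)/80. The values of m are assumptions, because the documents give no dropout rate.

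| m of 80 | True 10% reported as | True 20% reported as |
|---|---|---|
| 2 | 9.8% | 19.5% |
| 4 | 9.5% | 19.0% |
| 8 | 9.0% | 18.0% |

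In a group of 40, m = 2 gives the same proportional loss as m = 4 in a group of 80 (9.5% and 19.0%).

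**Outer bound.** If every uncollected subject had had an event, an observed 8/80 would become (8 + m)/80, which is 12.5%, 15.0% or 20.0% for m = 2, 4 or 8.

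**Where it does not apply.** For solicited reactions, a subject with no data leaves the denominator, so a missing card does not mechanically lower the rate.

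**The case against.** The strongest reply is that the dropouts who matter most for safety are already covered. Protocol 5.2.8 makes the investigator determine whether a voluntary withdrawal is due to safety concerns and, if so, record it as an SAE or other AE. Protocol 5.2.10 ranks the reasons so that voluntary withdrawal is the residual category, not due to an AE. Someone who leaves because of reactogenicity should therefore get full follow-up. This stands. A reader might infer that reactogenicity-driven dropouts are the least followed; the documents say the opposite, unless the reason is misclassified, and nothing in them shows that. What the reply does not cover is an AE that begins after a subject has left for another reason.

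A reader might also take the SAP footnotes to say that 28-day data exist for everyone who stops. They do not. They concern interrupting vaccination, which is not the same as leaving the trial. For contraindications, for instance, "Subjects will not be withdrawn due to contraindication but will be followed up for safety and possibly immunogenicity assessment", and Protocol 5.2.12 keeps pregnant subjects in safety follow-up. The footnotes mainly say under which visit AEs are recorded, and SAP 5.3.2 acknowledges that missing data come mostly from dropouts.

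Finally, the V08 date is a latest date. A site may call sooner, DC1 is reviewed at V02 and V03, and a card retrieved late may hold entries made at the time. Protocol 5.2.9 also requires repeated calls and certified mail when a subject fails to return. All of this makes loss less likely. None of it fixes a contact at the end of the 28-day window for a subject who has announced withdrawal.

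**Conclusion.** The point holds in a narrow form. For voluntary withdrawals not due to an AE who have not refused contact, the protocol permits a first contact roughly 5 to 6 months after the AE window closes and schedules no diary-card retrieval. If nothing is collected, the SAP denominator turns the gap into an absence of AEs. That conflicts with the SAP's stated principle on denominators.

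The documents do not support saying that these AEs will go uncollected or will rest on months-old recall; they show only that the plan allows it. The expected effect is small: 0.5 points at a 10% rate with 4 of 80 uncollected, against a CI of 4.4 to 18.8. A larger figure can be reached by assumption. For example, 4 to 8 subjects at event rates of 20% to 40%, all lost, gives 4 × 0.20/80 = 1.0 to 8 × 0.40/80 = 4.0 points. Neither the counts nor the rates have a source in the documents, and such a figure assumes total loss despite the V08 contact and the diary card. In the any-dose analysis the loss is smaller still for subjects already counted with an AE after an earlier dose. Nothing in the documents indicates that dropout differs between groups. This is a cheap improvement in ascertainment, not a flaw that threatens the trial's conclusions.

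**What to change.** - **Protocol 5.2.11:** for voluntary withdrawals who have not refused contact, attempt contact and retrieve the diary card at 28 (+3) days after the last injection actually received, to collect solicited reactions and unsolicited AEs. By last dose 1 to 5, the 28-day mark falls on D28, D31, D35, D42 or D56. Keep the V08 contact for SAEs and AESIs.
- **SAP 5.1.2.2.1 footnotes:** reconcile the dose-3 and dose-4 footnotes, which count from the first and second injections, with the endpoint in Protocol 9.2.2.
- **SAP safety tables:** report, per group, the number of vaccinated subjects without 28-day follow-up, so that a reader can see how many are counted as AE-free without data.

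The cost is protocol and SAP wording, one count per group, and one earlier call for the few subjects affected. Those who refuse contact are still left alone.

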5.2.12 Follow-up and Reporting of Pregnancies

Pregnancy is an exclusion criterion for enrollment in this study, but a subject could potentially become pregnant during her participation. In case of pregnancy and if at least one dose of the study vaccine(s) has been administered, the subject will not be discontinued from the trial and will be followed for safety assessment (and may be followed for immunogenicity assessment, if applicable). However, no additional vaccination will be administered.

All pregnancy cases should be reported if they occurred during the study. To report the pregnancy case, the Investigator must fill out an e- Pregnancy Reporting Form and inform the Sponsor within 1 month of identifying a pregnancy case.

Study staff must then maintain contact with the subject to obtain information about the outcome—i.e., details about the delivery and the newborn, or about pregnancy termination—and must update the Pregnancy Reporting Form, this time marking the “Follow-up” checkbox. This information should be provided to the Sponsor within 1 month of delivery.

Pregnancy itself is not considered an AE, but any complications during pregnancy are to be considered as AEs, and in some cases could be considered SAEs. Spontaneous abortions, fetal death, stillbirth, and congenital anomalies reported in the baby are always considered as SAEs, and the information should be provided to the Global Pharmacovigilance and Epidemiology (GPE) Department regardless of when the SAE occurs (e.g., even after the end of the trial).

5.3 Safety Emergency Call

If, as per the Investigator's judgment, a subject experiences a medical emergency, the Investigator may contact the Sponsor's Responsible Medical Officer (RMO) for advice on trial related medical question or problem. If the RMO is not available, then the Investigator may contact the Call Center - available 24 hours a day, 7 days a week - that will forward all safety emergency calls to the appropriate primary or back-up Sanofi Pasteur contact, as needed. The toll-free contact information for the Call Center is provided in the Operating Guidelines.

This process does not replace the need to report an SAE. The investigator is still required to follow the protocol defined process for reporting SAEs to GPE (Please refer to [Section 10](#)).

In case of emergency code-breaking, the Investigator is required to follow the code-breaking procedures described in [Section 6.5](#).

5.4 Modification of the Trial and Protocol

Any amendments to this trial plan and protocol must be discussed with and approved by the Sponsor. If agreement is reached concerning the need for an amendment, it will be produced in writing by the Sponsor, and the amended version of the protocol will replace the earlier version. All substantial amendments e.g., that affect the conduct of the trial or the safety of subjects, require IEC / IRB approval, and must also be forwarded to regulatory authorities.

An administrative / non substantial amendment to a protocol is one that modifies some administrative or logistical aspect of the trial but does not affect its design or objectives or have an impact on the subjects' safety. The IECs / IRBs must approve all amendments linked to administrative changes.

The Investigator is responsible for ensuring that changes to an approved trial, during the period for which IEC / IRB approval has already been given, are not initiated without IEC / IRB review and approval, except to eliminate apparent immediate hazards to subjects.

5.5 Interruption of the Trial

The trial may be discontinued if new data about the investigational product resulting from this or any other trials become available; or for administrative reasons; or on advice of the Sponsor, the Investigators, and / or the IECs / IRBs. If the trial is prematurely terminated or suspended, the Sponsor shall promptly inform the Investigators, the regulatory authorities, and the IECs / IRBs of the reason for termination or suspension, as specified by the applicable regulatory requirements.

The Investigator shall promptly inform the trial subjects and assure appropriate therapy and / or follow-up for them.

The SMT, led by the GSO and the Clinical Team Leader (CTL), will be responsible for the review, assessment and evaluation of safety data generated from this study. The occurrence of any related SAE or related death^a at any time during the recruitment period will trigger a suspension of enrollment and subsequent vaccination for the enrolled subjects. The FDA will be notified within 48 hours of assessment of the causal relationship of the case.

The SMT will then perform a full evaluation of the case and an analysis of circumstances around the events, and if no increased safety risk is concluded, will provide advice on the appropriate strategy to continue enrollment. The FDA will be notified within 48 hours about the SMT decision.

^a related cases as assessed by the Investigator and/or Sponsor medical monitor

6 Vaccines Administered

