5.1.3 Trial Plan

The trial plan is summarized in the [table of study procedures](#).

Recruitment and information of subjects:

Before inclusion in the trial, the Investigator will orally inform potentially eligible subjects about the trial. They will be given an oral description of the trial design, presenting the general benefits and risks related to the trial. They will be informed that they may return and receive further information and sign the full informed consent during the recruitment period. The process of subject recruitment and any oral or written information that will be provided to the subjects must be documented. This will be available in the Investigator's file and the Trial Master File.

It should be noted that subjects who may have been pre-screened may not necessarily be included in the trial if the required number of subjects have already been recruited.

Informed consent will be obtained before inclusion of the subject in the study (see [Section 5.2.2](#)).

Trial description:

After having signed the ICF and provided the initial blood sample, eligible subjects will be included in the study.

Eligible subjects will receive a total of 5 injections (1 injection at D0, D03, D07, D14 and D28) according to the Essen regimen for rabies post-exposure prophylaxis (PEP). HRIGs will be administered at D0 at the time of the first vaccine injection.

Subjects will be observed for safety for 30 minutes after each vaccination, and any AE/reaction occurring between each vaccination and up to 28 days after the fifth vaccination will be recorded by the subjects in a diary card (DC). The Investigator or delegate will transcribe the DC information into the electronic case report form (CRF) after interviewing the subject. In addition, all SAEs and AESIs will be recorded throughout the study, i.e., up to 6 months after the last injection.

Immunogenicity will be assessed in all subjects included in the trial, before the first vaccine injection (VAC1) (D0), before VAC4 (D14), before VAC5 (D28), 14 days after VAC5 (D42) and 6 months after VAC5 (M7). The RFFIT assay will be used for immunogenicity assessment.

Blood sampling:

All subjects will provide a total of five blood samples of 5-mL each, to assess the immune response induced by the rabies vaccines.

Table 5.3 below outlines the schedule of blood sampling and vaccine injection.

Table 5.3: Blood Sampling and Vaccination Schedule

	V01	V02	V03	V04	V05	V06	V07	V08

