- 9) Remind the subject to notify the site in case of an SAE or pregnancy (for woman of childbearing potential).
- 10) Complete the relevant source document information and CRF pages for this visit.

V04 (14 [± 1] days after VAC1): Collection of Safety Information, Blood Sample and Vaccination

- 1) Review and collect the DC1 with the subject, including any adverse events, medications, or therapy that occurred since vaccination by Investigator or delegate.
- 2) Urine pregnancy test, if applicable.
- 3) Conduct a physical examination, including temperature.

- 4) Obtain the second 5mL blood sample (see [Section 7.1](#) for detailed instructions regarding the handling of blood samples).
- 5) Check contraindication for subsequent vaccinations (see [Section 5.2.7](#)).
- 6) Call the Interactive Response Technology (IRT) system (IV/WRS) for randomization, dose number assignment and allocation of subject number (see [Section 6.6](#)).
- 7) Inject the appropriate study vaccine (VAC4) in the opposite arm as compared to the VAC3.
- 8) Keep the subject under observation for 30 minutes, and record any adverse reaction in the source document.
- 9) Give the subject the second diary card (DC2).
- 10) Remind the subject to notify the site in case of an SAE or pregnancy (for woman of childbearing potential).
- 11) Complete the relevant source document information and CRF pages for this visit.

V05 (28 [± 3] days after VAC1): Collection of Safety Information, Blood Sample and Vaccination

- 1) Review and collect the DC2 with the subject, including any adverse events, medications, or therapy that occurred since vaccination by Investigator or delegate.
- 2) Urine pregnancy test, if applicable.
- 3) Conduct a physical examination, including temperature
- 4) Obtain the third 5mL blood sample (see [Section 7.1](#) for detailed instructions regarding the handling of blood samples).
- 5) Check contraindication for subsequent vaccinations ([Section 5.2.7](#)).
- 6) Call the Interactive Response Technology (IRT) system (IV/WRS) for randomization, dose number assignment and allocation of subject number (see [Section 6.6](#)).
- 7) Inject the appropriate study vaccine (VAC5) in the opposite arm as compared to the VAC4.
- 8) Keep the subject under observation for 30 minutes, and record any adverse reaction in the source document.
- 9) Give the subject the third diary card (DC3).

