5.1.5 Planned Trial Calendar

The following dates are approximate. The actual dates may differ as, for example, the trial will not start until all the appropriate regulatory and ethical approvals have been obtained.

Planned trial period - FVFS ^a to LVLS ^a :	April 2017 – February 2018
Planned inclusion period - FVFS ^a to FVLS ^a :	April 2017 – May 2017
Planned vaccination period:	April 2017 – June 2017
Planned follow-up period:	June 2017 – February 2018
Planned end of trial:	February 2018
Planned date of final clinical trial report:	July 2018

The expected trial duration is 7 months for all subjects included in the trial.

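### Protocol 5.5: the trigger for the only automatic trial-wide pause stops at the end of recruitment, while dosing runs on for 28 days (31 at most)

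*Protocol*

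**What the plan says.** Protocol 5.5 makes the internal safety management team (SMT) responsible for reviewing the trial's safety data. It then sets one automatic rule: a related SAE or related death, as judged by the Investigator and/or the Sponsor's medical monitor, "at any time during the recruitment period will trigger a suspension of enrollment and subsequent vaccination for the enrolled subjects". Two FDA notices are attached. The first reads "The FDA will be notified within 48 hours of assessment of the causal relationship of the case"; the second follows within 48 hours of the SMT decision. If the SMT finds no increased risk, it "will provide advice on the appropriate strategy to continue enrollment".

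The recruitment period is not defined. Protocol 5.1.3 uses the term for the time in which candidates may return and "sign the full informed consent during the recruitment period". Protocol 5.1.5 keeps inclusion and vaccination apart: inclusion is planned for April to May 2017 and vaccination for "April 2017 – June 2017".

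On dosing, Protocol 5.1.3 states: "Eligible subjects will receive a total of 5 injections (1 injection at D0, D03, D07, D14 and D28) according to the Essen regimen". The fifth dose is due at "V05 (28 [± 3] days after VAC1" (Protocol 5.1.4).

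**The concern.** The action and the trigger in the 5.5 rule cover different periods. The action protects people who are part-way through the vaccine series. The trigger ends once nobody new is being included, when some subjects still have doses to come. On the last day of recruitment, one related SAE pauses dosing for everyone until the SMT has evaluated it. The same event a day later leaves that pause to discretion.

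This is a matter of subject safety. Three quarters of the subjects (240 of 320) receive VRVg-2. Protocol 3 plans no independent monitoring committee, has the SMT review blinded, and bases its reassurance on trials of VRVg-1. Protocol 1.4 says that all three VRVg-2 dosages carry more antigen per dose than VRVg-1. No readable text gives a reason for dropping the automatic pause while these subjects are still being dosed.

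**Working it through.** **1. Check against the plan's own calendar.** Inputs: inclusion ends in May 2017 and vaccination in June 2017 (5.1.5); VAC5 falls on day 28 ± 3 (5.1.4). If the last inclusion is on 31 May, the nominal last dose is 31 May + 28 days = 28 June, which agrees with the calendar. The window runs from 25 June (+25) to 1 July (+31). The plan therefore expects dosing after inclusion has closed.

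**2. Length of the uncovered interval.** Last inclusion to last dose is 28 days nominally and 28 + 3 = 31 at most. This needs no accrual assumption. On the day of inclusion the last subject has 5 − 1 = 4 doses to come.

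**3. Doses outstanding by time since inclusion, at nominal days.**

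| Included before closure | Doses outstanding |
|---|---|
| 0–2 days | 4 |
| 3–6 days | 3 |
| 7–13 days | 2 |
| 14–27 days | 1 |
| 28 days or more | 0 |

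Because VAC5 may be given from day 25, a dose is certain to be outstanding only for subjects included in the last 24 days.

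**4. Number of subjects (illustration only).** The documents give no accrual pattern. Assume 320 subjects accrue uniformly over L days and the event falls on the day of closure. The number still waiting for a dose due on day d is 320 × d / L.

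| Dose | d | L = 60 | L = 45 | L = 30 |
|---|---|---|---|---|
| VAC3 | 7 | 37 | 50 | 75 |
| VAC4 | 14 | 75 | 100 | 149 |
| VAC5, nominal | 28 | 149 | 199 | 299 |
| VAC5, all on day 25 | 25 | 133 | 178 | 267 |

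For example, 320 × 28 / 60 = 149. Every count falls to zero over the following 28 (at most 31) days.

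**5. Does another rule fill the interval?**
- Trial-level stops: the general discontinuation clause in 5.5, the synopsis entry on early safety data review, and 10.4 all say that the trial may be stopped or changed. None requires it.
- Subject-level stop: under 5.2.7.2 a vaccine-related SAE ends vaccination, but only for the affected subject.
- Reporting: SAEs go to the Sponsor within 24 hours (10.1) and to health authorities under local rules (10.5). Related SAEs go to the IEC/IRB (section 4).
- Other powers: changes may precede IEC/IRB approval to remove an immediate hazard (5.4), and the Investigator or Sponsor may withdraw subjects for safety (5.2.8).

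None of these restores an automatic pause for the other subjects.

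**The case against.** The strongest reply is that the interval is short and far from unprotected. SMT responsibility in 5.5 carries no recruitment limit, and every route in step 5 stays open. The Sponsor could pause dosing the same day. The protocol also expects few such events: 1.3.2 says that Verorab's identified and potential risks have not been seen with VRVg specifically, and section 3 expects no major safety issue from the reformulation. This stands and lowers the weight. It does not close the gap, because what remains at trial level is discretion or reporting, and the expectation rests partly on VRVg-1.

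The recruitment period is also undefined, and its use in 5.1.3 is incidental. The limit may be loose drafting, or it may be deliberate. Either way a clarification is needed.

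The restart sentence is mainly a wording point. It follows a suspension of both enrollment and vaccination, and the SMT decision can naturally be read as resolving both.

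Three stronger readings are tempting, and the documents do not support them:
- **That the suspension itself expires with recruitment, so that the last subject is protected for only one dose of five.** Only the trigger is time-limited. The action has no end date, so an event on the last inclusion day would also hold back that subject's remaining four doses.
- **That safety oversight stops at closure.** Step 5 shows that it does not.
- **That a known, large number of subjects is exposed.** The counts in step 4 rest on assumed uniform accrual and an event exactly at closure. Only the 28- and 31-day figures come from the documents.

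**Conclusion.** The point holds in limited form. As 5.5 is written, a related SAE or related death after the last inclusion meets no automatic trial-wide trigger, although vaccination continues for 28 days (31 at most). What is lost is the default pause for the other subjects and the linked 48-hour FDA notices. A pause already in force continues.

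This rests on reading the recruitment period as ending at the last inclusion. That is the natural reading of 5.1.3 and 5.1.5, but it is not a stated definition. The documents give no rate for related SAEs, so the chance of one in this interval is not estimated here. The gap itself affects no endpoint, estimate or sample-size figure. The weight is minor to moderate: a cheap improvement in subject safety.

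**What to change.** In Protocol 5.5:
- Replace the recruitment limit on the trigger with *at any time from the first vaccination until the last vaccination of the last subject*.
- In the restart sentence, let the SMT advice cover continuing *enrollment and/or vaccination*.
- Require that advice to say whether doses falling due during a suspension are given late or omitted. The visit windows cannot settle this: the protocol's Table of Study Procedures gives V02 no tolerance and V03 only +1 day. The only postponement rule, 5.2.7.1, is for illness.

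If the limit is deliberate, state the reason in 5.5 instead.

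**Cost.** Made after approval, this is a substantial amendment needing IEC/IRB approval and forwarding to regulators (5.4). Other costs arise only if a pause occurs after closure:
- *D14 per-protocol set (12.2.3).* A subject is lost if VAC2 falls after D5, VAC3 falls after D9, one of the first three doses is omitted, or the sample falls outside D13–D15. In V04 the step "Obtain the second 5mL blood sample" precedes VAC4. If that draw is kept on schedule, the loss is limited to subjects still waiting for VAC3 (37 to 75 under the step 4 assumptions for 60 to 30 days). If the visit slips with the dose, it could reach those waiting for VAC4 (75 to 149).
- *Full analysis set.* Late or omitted doses stay in the analysis, because all available data are used (12.2.1). VAC4 affects D28, D42 and M7; VAC5 affects D42 and M7. This matters because section 12 bases dose choice on all timepoints.

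The protocol already accepts the same kind of cost for a pause during recruitment.
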